10.4.3 Pharmacokinetic Analyses

The plasma, urine, and CSF WVE-120101 concentration as well as WVE-120101-related metabolite data will be summarized for patients in the PK population.

The individual patient plasma and urine concentration-time data will be listed and displayed graphically on linear and log scales. The plasma and urine concentration-time data will be summarized descriptively in tabular and graphical formats (linear and log scales).

For each dose group, the plasma and urine WVE-120101 concentration data will be analyzed by noncompartmental PK analysis. The parameters listed in [Table 6](#) will be determined. Additional PK parameters may be evaluated if deemed appropriate. Pharmacokinetic parameters for each dose group will be summarized for each WVE-120101 dose level.

The CSF concentration data will be summarized in tabular format.

Table 6 Pharmacokinetic Parameters of WVE-120101 after Multiple Dose Administration

Parameter	Definition
C_{\max}	Maximum observed concentration
t_{\max}	Time of occurrence of C_{\max}
$AUC_{0-\tau}$	Area under the plasma concentration-time curve over the dosing interval
AUC_{last}	Area under the plasma concentration-time curve from time 0 to the last measurable concentration.

10.4.4 Clinical Effects and Pharmacodynamic Analyses

The change from baseline for clinical effects and PD endpoints will be summarized using a mixed model for repeated measures (MMRM) with the safety population. The MMRM will include the relevant baseline measure, time, dose-group and time by dose-group interactions. The MMRM will be used to construct 95% confidence intervals and to test if the change is statistically significant. Summaries will be based on data collected during the OLE and, separately, OLE data integrated with repeat dosing data from [WVE-HDSNP1-001](#).

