
9. Clinically significant cardiovascular, endocrine, hepatic, renal, pulmonary, gastrointestinal, neurologic, malignant, metabolic, psychiatric, or other condition that, in the opinion of the Investigator, precludes the patient's safe participation in the study or would interfere with the study assessments.
 
10. Bone, spine, bleeding, or other disorder that exposes the patient to risk of injury or unsuccessful lumbar puncture.
 
11. Inability to undergo brain MRI (with or without sedation).
 
12. In the opinion of the Investigator, deemed to be at significant risk for suicidal behavior.
 
13. Involved directly or indirectly in the conduct and administration of this study as an Investigator, sub-investigator, study coordinator, or other study staff member, or the patient is a first-degree family member, significant other, or relative residing with one of the above persons involved directly or indirectly in the study.
 
14. Anticipates using antiplatelet or anticoagulant therapy during the course of the study. Patients who received antiplatelet or anticoagulant therapy must complete one of the following washout periods before the Screening Visit:
 
 A 7-day washout period for antiplatelet therapy, A 1-day washout period for anticoagulants (except warfarin), or A 5-day washout period for warfarin. 			

Investigational Product, Dose, Route, Regimen: WVE-120101. Patients will receive ≥ 16 mg (not to exceed the maximum dose and frequency described in the Phase 1b/2a protocol (WVE-HDSNP1-001) approved in each country). The investigational product will be supplied as a lyophilized powder that will be reconstituted into an injectable solution. The route of administration of the reconstituted WVE-120101 solution will be IT injection by direct lumbar puncture.
			

Reference Therapy, Dose, Route, Regimen: Not applicable. All patients will receive WVE-120101.
			

Study Duration: The planned duration is 101 weeks. Patients will receive doses every 4 weeks over a period of 97 weeks, then complete a safety follow-up phase.
			

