2.1 Rationale for the Doses, the Dosing Regimen, and Route of Administration

This is an open-label extension study for the Phase 1b/2a clinical study WVE-HDSNP1-001. The clinical starting dose in WVE-HDSNP1-001 was selected in consideration of the data from both single- and 13-week repeat-dose toxicology studies; an animal model possessing the SNP1 variant targeted by WVE-120101 was not available to the Sponsor. The clinical starting dose of 2 mg was based on the no-adverse-effect-level (NOEL) for transient limb dysfunction in monkeys, which is considered the most relevant species for the purposes of clinical assessment. The lack of findings in the monkey at a dose of 2 mg provides a 10-fold safety margin to the HED, on the basis of relative CSF volume. Subsequent doses are selected based on safety assessments from each cohort.

In the original OLE study protocol, patients who were in the 2 and 4 mg dose cohorts in the Phase 1b/2a study were enrolled into the 4 or 8 mg dose group in this study. Patients who were in the 8 and 16 mg dose cohorts in the Phase 1b/2a study were enrolled into the 8 or 16 mg dose groups, respectively in this study. As of this amendment, patients will receive 16 mg or a higher dose of WVE-120101 in this study. The maximum dose and frequency in this OLE study in a given country will not exceed the maximum dose and frequency described in the Phase 1b/2a protocol (WVE-HDSNP1-001) approved in that country. If a dose lower than the maximum dose described in the Phase 1b/2a study is chosen for multiple dosing based on the safety review of the Phase 1b/2a study data by the Dose Escalation Committee (DEC) and Safety Monitoring Committee (SMC), that dose will be used in this OLE study.

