Based on the SMC and DEC review of Phase 1b/2a safety data, the highest tolerated dose level and/or a lower dose level may be selected for multiple dosing and further evaluation in the OLE. If one dose level is selected, all patients will be switched to receive treatment at that dose level. If more than one dose is selected, patients will be randomized 1:1 to the highest tolerated dose and one lower dose to be determined by the DEC in agreement with the SMC (Figure 2). The randomization will be stratified by cohort and use a fixed block size. These doses may be further revised based on emerging safety, PD, or clinical effects data in the Phase 1b/2a study. The maximum dose and frequency in this OLE study will not exceed the maximum dose and frequency described in the Phase 1b/2a protocol (WVE-HDSNP1-001) approved in each country.

Dose modification will occur at the next scheduled visit from the date of implementation of this amendment (Amendment 1.0). In addition to the assessments performed at every dosing visit, the Unified Huntington's Disease Rating Scale (UHDRS) and clinical laboratory evaluations should be performed at the visit when a dose is changed. Patients will not be asked to restart the treatment phase but will continue to receive doses as originally scheduled, every 4 weeks, at the new dose level.

Figure 2 Dose Modification Scheme

Abbreviations: DEC=Dose Escalation Committee; SMC=Safety Monitoring Committee

*Dose modification randomization. Applicable if 2 doses are studied.

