5 PATIENT SELECTION AND WITHDRAWAL CRITERIA

Approximately 50 patients will be enrolled. Patients will be assigned to study treatment only if they qualify according to all of the following inclusion and exclusion criteria. During Screening, patients who do not meet all remaining inclusion/exclusion criteria will be considered screen failures. Patients who fail screening may be rescreened once if the reason for screen failure is transient and the patient is expected to return to normal after recovery.

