10 STATISTICAL CONSIDERATIONS

10.1 Sample Size Determination

No sample size calculations were performed. As this is an OLE, the maximum sample size is fixed by the number of patients completing the WVE-HDSNP1-001 study.

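### Section 10.4.4 takes the CI and test of change from an MMRM with baseline as a covariate; for mean change within a dose group, the standard error is too small whenever change depends on baseline

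*Combined protocol and SAP*

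**What the plan says.** Section 10.4.4 states: "The change from baseline for clinical effects and PD endpoints will be summarized using a mixed model for repeated measures (MMRM) with the safety population". On the model terms: "The MMRM will include the relevant baseline measure, time, dose-group and time by dose-group interactions". On inference: "The MMRM will be used to construct 95% confidence intervals and to test if the change is statistically significant". The synopsis repeats the first and last of these. The analysis is done on OLE data and, separately, on OLE data integrated with repeat-dosing data from the parent study.

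The synopsis gives no reference therapy: "All patients will receive WVE-120101". Section 5 says "Approximately 50 patients will be enrolled", and section 10.1 says "No sample size calculations were performed".

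Dose groups can arise in three ways.

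- Section 4.1: "If one dose level is selected, all patients will be switched to receive treatment at that dose level".
- Section 4.1: if more than one dose is selected, patients are randomised 1:1, stratified by cohort.
- Section 2.1, describing the OLE before the amendment: dose followed the parent cohort. For example, "Patients who were in the 8 and 16 mg dose cohorts in the Phase 1b/2a study were enrolled into the 8 or 16 mg dose", each cohort going to its matching level.

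The plan does not say whether the test is within or between dose groups, at which baseline value the adjusted mean is evaluated, or how its standard error is obtained.

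**The concern.** Adjusting for baseline is sound for a difference between dose groups, because the term for the baseline mean cancels. It does not cancel for a change within one group. The model then estimates the expected change for a patient at the observed mean baseline and treats that mean as a known constant. If the intended quantity is the mean change in the population that the dose group represents, the sampling error of the baseline mean is left out and the interval is too short.

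A second effect needs dose groups that were not formed by randomisation. An adjusted mean evaluated at the pooled baseline moves each group away from its own mean change.

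This model gives the only inference stated for the clinical and PD endpoints. Both effects can make a change look significant when mean change is zero, and there is no control arm to reveal it.

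**Working it through.** The plan states no figure to reproduce beyond the 95% level, so the check is whether that level holds when mean change is zero.

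**Inputs.** From the documents: N about 50 (section 5), the model terms (section 10.4.4), and one dose group or two randomised 1:1 (section 4.1). The 95% CI implies a two-sided 5% test. Assumed, because the documents are silent: rho from 0.5 to 0.9, the ratio k of follow-up SD to baseline SD (1 or 1.2), complete data, and baseline gaps between cohorts.

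**Step 1: standard error, one group.** Let the baseline SD be σ. The slope of change on baseline is b = k·rho − 1. The model reports a variance of k²σ²(1 − rho²)/n. For mean change the true variance adds b²σ²/n. With k = 1:

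- reported: σ²(1 − rho²)/n
- true: 2σ²(1 − rho)/n
- ratio of variances: (1 + rho)/2

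The large-sample rejection rate is 2[1 − Φ(1.96 × SE ratio)]. The last two columns are simulated (n = 50, single visit, 100,000 trials, Monte Carlo error about 0.1 point).

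| rho | SE ratio | Formula | Simulated, covariate model | Simulated, one-sample t |
|---|---|---|---|---|
| 0.5 | √0.75 = 0.866 | 9.0% | 8.8% | 5.1% |
| 0.7 | √0.85 = 0.922 | 7.1% | 7.0% | 5.1% |
| 0.8 | √0.90 = 0.949 | 6.3% | 6.1% | 4.9% |
| 0.9 | √0.95 = 0.975 | 5.6% | 5.5% | 5.0% |

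Repeated-measures fits behave similarly. A four-visit MMRM with unstructured covariance (3,000 trials) covered mean change 91.5% of the time at rho 0.5 and 93.9% at 0.8. An eight-visit version (1,500 trials) rejected 9.3%, 6.7% and 5.0% at rho 0.5, 0.7 and 0.8.

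**Step 2: unequal SDs.** With k = 1.2, b = 1.2·rho − 1, which is −0.40, −0.16 and −0.04 at rho 0.5, 0.7 and 0.8. Simulated rejection falls to 6.6%, 5.5% and 4.9%. When b = 0 (for example rho 0.8 with k = 1.25) there is no error.

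**Step 3: two randomised groups of 25, k = 1.** The omitted term is b²σ²/N with N = 50, while each group's own variance is divided by 25, so the omission matters less. Simulated rejection is 6.8% at rho 0.5 and 5.6% at 0.8.

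**Step 4: point estimate.** With one dose group and complete data, the pooled mean baseline is the group's own mean, so the adjusted mean equals the raw mean change. With two randomised groups they differ by chance imbalance only.

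**Step 5: non-randomised groups, k = 1.** Evaluated at the pooled baseline, a group with zero true change shows an apparent change of (1 − rho) times its distance from that baseline. For two groups of 25 whose population baselines are 0.5 SD apart, each lies 0.25 SD from the pooled mean:

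- rho 0.5: shift 0.5 × 0.25 = 0.125 SD, reported SE about √(0.75/25) = 0.173, simulated rejection 12.4%
- rho 0.8: shift 0.2 × 0.25 = 0.05 SD, reported SE about √(0.36/25) = 0.12, simulated rejection 7.5%

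A one-sample test on the group's own change stayed at 4.9% to 5.0% in both settings.

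**The case against.** The strongest reply is that section 10.4.4 never defines the target. If the target is change at the observed mean baseline, the interval is correct: coverage for it was 94.2% to 95.3% in every setting of the MMRM simulation. This stands, so the point is conditional on wanting mean change within a dose group. But the plan does not name the conditional target, and with no control arm most readers will take the change to mean mean change.

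A reader might infer that the model estimates something other than the dose group's mean change, and that its intervals are always too narrow. The documents support neither. The estimate is unaffected with one dose level and complete data, and differs only by chance under randomisation. The intervals have the right width for mean change when change does not depend on baseline.

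It can also be said that the baseline gaps between cohorts are hypothetical, that evaluation at the pooled mean is a usual default and not plan text, and that cohort-based dosing belongs to the OLE before the amendment. All of this is true, so the shift is a possibility and not a demonstrated bias. It stays relevant because the integrated analysis includes parent repeat-dosing data, and because the plan does not say how dose group is coded for patients whose dose changes.

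Finally, the primary objective is safety, analysed descriptively, and section 10 attaches no decision rule to these tests. That limits the priority.

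**Conclusion.** The concern holds in a limited form. If the target is mean change within a dose group, the stated model with its usual standard error gives intervals that are too narrow whenever change depends on baseline. For one group of 50 with equal SDs, the error rate is about 9% at rho 0.5, 7% at 0.7, 6% at 0.8 and near nominal at 0.9. It is lower if the SD grows over follow-up or if there are two randomised groups. The shift in the estimate arises only where dose groups were not randomised, differ at baseline, and are evaluated at the pooled mean. With a 0.5 SD gap, the error rate is then about 12% at rho 0.5 and 7.5% at rho 0.8. The values of rho, the SD ratios and the gaps are all assumptions. For endpoints with rho near 0.9, the standard-error effect is negligible. This is a modest weakness in secondary analyses.

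**What to change.** In section 10.4.4, with the synopsis kept in line:

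- State that the target is the mean change from baseline within each dose group.
- Take its 95% CI and test from a repeated-measures model with the baseline value as the first response, using the visit-minus-baseline contrast within dose group.
- Keep the baseline-covariate MMRM for differences between dose groups, and state the baseline value at which its adjusted means are evaluated.

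This costs a short change of analysis wording and a small program change, with no new data, patients or procedures. The downside is wider intervals. With one group and equal SDs they widen by a factor of 1/0.949 = 1.05 at rho 0.8 and 1/0.866 = 1.15 at rho 0.5, which is the correct width for mean change. A simpler alternative is to report the unadjusted mean change and its CI beside the model estimate.

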11 REGULATORY, ETHICAL, AND LEGAL OBLIGATIONS

11.1 Declaration of Helsinki

The Sponsor and Investigator(s) will ensure that this study is conducted in accordance with the most recent revision of the Declaration of Helsinki.

11.2 Good Clinical Practice

The Study will be conducted according to the study protocol and SOPs that meet the guidelines provided by the International Conference on Harmonisation (ICH) for Good Clinical Practice (GCP) in clinical studies, and any other applicable local regulatory requirements.

11.3 Institutional Review Boards/Ethics Committees

Federal regulations and ICH guidelines require that approval be obtained from an IRB or EC before participation of human patients in research studies. Before study onset, the protocol, informed consent form, advertisements to be used for the recruitment of study patients, and any other written information regarding this study to be provided to the patient or the patient's legal guardian must be approved by the IRB or EC. Documentation of all IRB/EC approvals and of the IRB/EC compliance with ICH guideline E6(R2): GCP will be maintained by the site and will be available for review by the Sponsor or its designee.

All IRB/EC approvals should be signed by the chairman or designee and must identify the IRB/EC name and address, the clinical protocol by title or protocol number or both, and the date approval or a favorable opinion was granted. The study protocol, appendices, and ICFs must be approved by the IRB/EC.

The Investigator is responsible for providing written summaries of the progress and status of the study at intervals not exceeding one year or otherwise specified by the IRB/EC. The Investigator must promptly supply the Sponsor or its designee, the IRB/EC, and, where applicable, the institution, with written reports on any changes significantly affecting the conduct of the study or increasing the risk to patients.

11.4 Informed Consent Forms

Signed ICFs in compliance with the Declaration of Helsinki, current ICH and GCP guidelines, US Title 21 Code of Federal Regulations (CFR) Part 50, and applicable local regulations will be obtained from each patient before enrolling the patient in the study or performing any unusual or non-routine procedure that involves risk to the patient. Due to the natural progression of the disease, patients may lose the ability to understand the ICF after providing original consent. As a result, patients should identify a potential legally authorized representative at Screening.

Informed consent form templates will be provided by the Sponsor to investigative sites. If any institution-specific modifications to study-related procedures are proposed or made by the site, the ICF(s) must be reviewed by the Sponsor or its designee or both before IRB/EC submission. Once reviewed, the ICF(s) will be submitted by the Investigator to his or her IRB/EC for review and approval before the start of the study. If the ICF(s) is revised during the course of the study, all actively participating patients or their legally authorized representatives must sign the revised form.

Before Screening, each prospective patient will be given a full explanation of the study and be allowed to read the approved ICF. Once the Investigator is assured that the patient understands the implications of participating in the study, the patient will be asked to give consent to participate in the study by signing the appropriate ICF.

In addition to signing the approved ICF, patients will be asked to sign a supplementary consent form to specify whether or not they agree to allow their leftover samples to be stored and used for future medical or pharmaceutical research regarding Huntington's disease.

The Investigator will retain the signed original ICF(s) and give a copy of the signed original form(s) to the patient and/or their legally authorized representative.

11.5 Specimen Management and Storage

Samples will only be used by the Sponsor and/or a contracted vendor for research related to the development of treatments for HD and stored for a maximum of 15 years. All biological material will be stored and secured in a way that ensures that unauthorized access is prohibited and the samples are not lost, deteriorated, or destroyed accidentally or illegally. Detailed instructions for sample collection, storage, processing, and shipping will be provided in the study-specific manual.

12 INVESTIGATOR'S OBLIGATIONS

The following administrative items are meant to guide the Investigator in the conduct of the study in accordance with GCP guidances. These items may be subject to change based on industry and government SOPs, working practice documents, or guidelines. Changes will be reported to the IRB/EC but will not result in protocol amendments.

12.1 Confidentiality

All laboratory specimens, evaluation forms, reports, and other records will be identified in a manner designed to maintain patient confidentiality. All records will be kept in a secure storage area with limited access. Clinical information will not be released without the written permission of the patient, except as necessary for monitoring and auditing by the Sponsor, its designee, applicable regulatory agencies, or the IRB/EC.

The Investigator and all employees and coworkers involved with this study may not disclose or use for any purpose other than performance of the study any data, record, or other unpublished confidential information disclosed to those individuals for the purpose of the study. Prior written agreement from the Sponsor or its designee must be obtained for the disclosure of any said confidential information to other parties.

12.2 Investigator Documentation

Prior to beginning the study, the Investigator will be asked to comply with ICH E6(R2) 8.2 and Title 21 of the United States Code of Federal Regulation by providing the following essential documents, including but not limited to:

- IRB/EC approval
- A fully executed Clinical Study Agreement
- Curriculum vitae for the Investigator and each sub-investigator listed on the IRB/EC application
- Financial disclosure information, as applicable
- IRB/EC-approved informed consent, samples of site advertisements for recruitment for this study, and any other written information regarding this study that is to be provided to the patient
- Laboratory certifications and normal ranges for any local laboratories used by the site

12.3 Study Conduct

The Investigator agrees that the study will be conducted according to the principles of ICH E6(R2). The Investigator will conduct all aspects of this study in accordance with all national, state, and local laws or regulations. Study information from this protocol will be posted

on publicly available clinical study registers in accordance with all national, state, and local laws or regulations.

A record of patient screen failures will be maintained for patients who do not qualify for enrollment, including the reason for the failure.

12.4 Adherence to Protocol

The Investigator agrees to conduct the study as outlined in this protocol in accordance with ICH E6(R2) and all applicable guidelines and regulations.

